3.1.4. Delivery Phase

Operational procedures will be instituted to optimize data collection and reporting consistency in those situations where the subject's delivery is performed by her referring primary care obstetrician. These procedures include identification at conclusion of Inpatient Randomized Treatment Phase of the intended delivery caregiver, ensuring the delivery caregiver or neonatal intensive care unit (NICU) staff understand the information needed for the study, those events that require rapid communication to clinical investigators, and a process that ensures clinical investigators can contact the appropriate personnel in case of follow-up questions.

For subjects who deliver at the investigative center, a placental tissue sample will be obtained at the time of delivery for central histopathologic examination and a cord blood sample will be collected for potential genetic research and biomarker assays. If delivery occurs within 12 hours of IP completion or discontinuation, the cord blood sample will also be used for the PK assessment (see SPM for information about how these samples will be collected), and, if required, a corresponding maternal blood sample will be collected for PK analysis (see Section 6.5.1). In addition, a breast milk/colostrum sample will be collected for PK analysis in women who deliver at the investigative center and produce breast milk within 12 hours after IP completion or discontinuation (see Section 6.5.3).

The following information regarding the delivery and hospitalization for mother and newborn will be obtained through a review of the hospital records:

- Date and time of delivery
- Mode of delivery
- Indication for delivery
- Concomitant medications
- Maternal AEs and serious AEs (SAEs) (including AEs of special interest; Section 6.3.2.3)
- Maternal health care resource use

The newborn medical records will also be reviewed in order to record the following:

- Variables relevant to the composite
- Apgar scores at 1 and 5 minutes
- Length, weight, and head circumference
- Blood gases (when available)

- Hospital length of stay
- Neonatal health care resource use
- Neonatal AEs and SAEs; in particular, the review will focus on any complications requiring intensive or specialized care and information specific to complications of prematurity will be collected (see Section [6.3.2](#) and Section [6.3.7.2](#)).

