6.2.4. Key Secondary Efficacy Endpoints

- Proportion of births prior to $37^{0/7}$ weeks' gestation – ascertain the GA at delivery based on a records review
 - Proportion of births at term ($37^{0/7}$ to $41^{6/7}$ weeks' gestation) – ascertain the GA at delivery based on a records review
 - Length of neonatal hospital stay – confirm duration (in days) of neonatal hospital admission from the medical records
 - Proportion of neonates with any diagnosis from the neonatal morbidity and mortality composite determined up to 28 days after EDD (of $40^{0/7}$ weeks) – proportion of infants with any one of the following:
 - Fetal or neonatal death
 - RDS
 - Requiring continuous positive airway pressure or mechanical ventilation. Diagnosis requires a chest radiograph consistent with RDS (reticulogranular appearance to the lung fields or air bronchograms) within the first 24 hours of life
- OR
- Received surfactant for a clinical picture of RDS within the first 24 hours of life

- Bronchopulmonary dysplasia at ≥ 36 weeks postmenstrual age (determined by adding chronological age to GA at delivery), defined as follows:
 - >21% supplemental oxygen requirement
 - OR
 - Use of high-flow nasal cannula at ≥ 1 L (21% oxygen)
- Necrotizing enterocolitis or isolated perforation
 - Diagnosed by radiographic evidence of Stage II or higher according to Bell's staging criteria (fixed/unchanging bowel loops, pneumatosis intestinalis, portal venous gas, pneumoperitoneum)
 - OR
 - Pneumatosis intestinalis, bowel necrosis, or perforation noted at surgery
- Sepsis based on positive blood culture with clinical features of sepsis
- Meningitis based on positive cerebrospinal fluid culture performed as part of infection workup
- Retinopathy of prematurity
 - Confirmed by an ophthalmologist based on international committee Stage 4 or 5
 - OR
 - Requiring surgical treatment with laser or other surgical intervention including cryotherapy or treatment with anti-VEGF (vascular endothelial growth factor)
- IVH
 - Grade 3 or 4 (severe IVH)
 - OR
 - Any grade of IVH with posthemorrhagic hydrocephalus requiring a shunt
- White matter injury, documented on cranial ultrasound or magnetic resonance imaging, as indicated by the following:
 - Multiple cystic lucencies in periventricular white matter (may be bilateral or unilateral, may vary in size, and be diffuse or focal in distribution)
 - OR
 - Porencephalic cyst (not including subependymal or choroid plexus cysts)
 - OR

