6.4.2. Health Outcomes – Neonatal

6.4.2.1. Neonatal Hospital Admission

For the delivery visit hospitalization, the length of the hospital stay (days) and associated hospital unit (NICU, nursery level, or level of care 1 to 4) will be recorded. In addition, whether the baby was transported to a different hospital or extended stay facility and length of stay (days) and number of hospital readmissions in the month following discharge from the delivery visit hospitalization will also be captured.

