5.2. Multiplicity Adjustment

There will be no multiplicity adjustment due to early termination of the study.

No formal tests of hypothesis will be performed on safety data.

Table 1 provides an overview of appendices within the RAP for outlining general considerations for data analyses and data handling conventions.

Table 1 Overview of Appendices

Section	Component
11.1	Appendix 1: Protocol Deviation Definitions
11.2	Appendix 2: Time and Events
11.3	Appendix 3: Treatment States and Phases
11.4	Appendix 4: Data Display Standards & Handling Conventions
11.5	Appendix 5: Derived and Transformed Data
11.6	Appendix 6: Premature Withdrawals & Handling of Missing Data
11.7	Appendix 7: Primary and Sensitivity Analyses for Primary and Key Secondary Endpoints with Missing Data
11.8	Appendix 8: Values of Potential Clinical Importance
11.9	Appendix 9: Model Checking and Diagnostics for Statistical Analyses
11.10	Appendix 10: Abbreviations & Trade Marks
11.11	Appendix 11: List of Data Displays

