8.1.2. Planned Key Secondary Efficacy Statistical Analyses

Key Secondary Efficacy Statistical Analysis	
Endpoint	
	
 • Proportion of births prior to $37^{0/7}$ weeks' gestation • Proportion of births at term ($\geq 37^{0/7}$ weeks' gestation) • Length of neonatal hospital stay • Proportion of neonates with any diagnosis from the neonatal morbidity and mortality composite determined up to 28 days after EDD (of $40^{0/7}$ weeks) (details for each composite are provided in Section 11.5.4.)

To preserve the overall type I error rate, the key secondary analysis will be performed if and only if the null hypothesis of the primary endpoint is rejected. In addition, a sequential testing method will be used to adjust for multiplicity of the key secondary endpoints such that the type I error rate will be maintained at 5%. The sequential testing examines the hypothesis testing in a pre-specified order, i.e., the testing of the second secondary endpoint will be performed only if the first secondary endpoint is significant at 5%, and testing of the third secondary endpoint will be performed only if the first and second endpoints are significant at 5%.
 
Order of sequential testing is
 
 1) Length of neonatal hospital stay 2) Proportion of births prior to $37^{0/7}$ weeks' gestation and Proportion of births at term 3) Neonate composite outcome 	
Model Specification	

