- For the delivery visit hospitalization, the length of the hospital stay (days) and associated hospital unit (NICU, nursery level, or level of care 1 to 4) will be recorded. The length of stay is calculated as the days between the delivery date/time and discharge date/time.
- In addition, whether the baby was transported to a different hospital or extended stay facility and length of stay (days) and number of hospital readmissions in the month following discharge from the delivery visit hospitalization will also be captured and reported.

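### Length of neonatal stay covers the birth admission only, so on the natural reading a newborn moved to another hospital has the stay cut off at transfer

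*SAP*

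**What the plan says.** Protocol 6.2.4 lists length of neonatal hospital stay as a key secondary endpoint and describes it only as "confirm duration (in days) of neonatal hospital admission from the medical records". It does not mention transfer.

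The derivation is in SAP 11.5.4, under the calculation of neonatal hospital admission. It refers to the birth admission and states: "The length of stay is calculated as the days between the delivery date/time and discharge date/time". The next item begins "In addition, whether the baby was transported to a different hospital or extended stay facility and length of stay (days", goes on to readmissions in the month after discharge, and says that these will be captured and reported. Protocol 6.4.2.1 makes the same split. It starts with "For the delivery visit hospitalization, the length of the hospital stay (days) and associated hospital unit" and then treats transport and the stay that follows as further items.

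SAP 8.1.2 analyses stay on the log10 scale by analysis of covariance, with a Wilcoxon rank sum test if the data are not log-normal. Table 2.301 in SAP 11.11.3 keeps this analysis on the shortened display list. SAP 8.1.2 also places the endpoint at the head of the sequential order ("1) Length of neonatal hospital stay"), but SAP 5.2 says: "There will be no multiplicity adjustment due to early termination of the study".

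**The concern.** The endpoint should reflect how long the infant needed hospital care. A transfer between hospitals does not end that need, but the derivation appears to stop the clock there. The infants affected are likely to include those needing care that the birth hospital cannot give, or those moved to another hospital to complete recovery, so the shortening would fall on long stays. An infant transferred on the first day could rank below a healthy term newborn.

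Transfer is foreseeable. Both documents collect it, and Protocol 3.1.4 makes arrangements for collecting data "in those situations where the subject's delivery is performed by her referring primary care obstetrician". At stake are the model-adjusted stays, the treatment difference, its confidence interval and its p-value.

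**Working it through.** **Text check.** The documents contain no figure that depends on this point, so there is nothing to reproduce. The question is whether any other section repairs the derivation.

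- Protocol 6.2.4 and SAP 2.2 define the endpoint as the duration of admission and are silent on transfer.
- SAP 11.7.4 imputes missing stays. A transferred infant with a recorded discharge from the birth hospital is not missing.
- The Wilcoxon fallback in SAP 8.1.2 would still rank that infant among the shortest stays.
- SAP section 9 says readmission stay is listed, not analysed.
- No section adds the stay after transfer, defines discharge as final discharge, or plans a sensitivity analysis for transferred infants.

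**Size of truncation.** All inputs here are assumptions: a true stay of 30 days, a recorded stay of 1 day (early transfer) or 20 days (late transfer), and a share f of infants affected. On the log10 scale each affected infant loses log10(30/1) = 1.48 or log10(30/20) = 0.18. The geometric mean is multiplied by (recorded/true)^f:

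| f | 30 cut to 1 | 30 cut to 20 |
|---|---|---|
| 2% | 0.934 (down 7%) | 0.992 (down 1%) |
| 5% | 0.844 (down 16%) | 0.980 (down 2%) |
| 10% | 0.712 (down 29%) | 0.960 (down 4%) |

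**Effect on the arm comparison.** Further assumptions: 50% of newborns sick on atosiban and 40% on retosiban, well newborns stay 3 days, sick newborns truly stay 30 days, and a share t of sick newborns in both arms is transferred on day 1. The difference in log10 means (retosiban minus atosiban) is

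(0.40 − 0.50) × [(1 − t) × log10(30) + t × log10(1) − log10(3)] = −0.10 × [(1 − t) × 1.477 − 0.477].

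| t | log10 difference | ratio of geometric means |
|---|---|---|
| 0 (whole stay counted) | −0.100 | 0.79 |
| 10% | −0.085 | 0.82 |
| 20% | −0.070 | 0.85 |
| 30% | −0.056 | 0.88 |
| 50% | −0.026 | 0.94 |

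With true sick stays of 20 to 60 days and transfer on day 1 or 2, the ratio moves the same way. At t = 30% it goes from 0.83 to 0.89–0.91 (20 days) and from 0.74 to 0.82–0.84 (60 days).

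With a within-group SD of 0.25 log10 (also assumed), power at two-sided 5% and 150 per arm falls from 35% at t = 0 to 13% at t = 30%. With about 48 per arm (97 randomized, SAP 2.3) it falls from 14% to 7%.

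**The case against.** The SAP never says that a transfer counts as a discharge. The protocol endpoint is the duration of hospital admission, and the newborn record review runs to 28 days after the estimated date of delivery, so a programmer could take discharge to mean final discharge. This stands as a limit on the claim. It does not remove the problem, because the derivation is tied to the birth admission and the later stay is booked separately. Two programmers could produce different values.

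A reader might infer that every transferred newborn is scored as a very short stay. Only an early transfer does that; a late one costs little, as the 30-to-20 column shows.

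A reader might also infer a false treatment benefit. If 10% are transferred in one arm and 5% in the other, with identical true stays and 30 days cut to 1, the arm with more transfers looks 16% shorter (30^−0.05 = 0.844). The documents do not support this as the expected result. If treatment changes transfer by changing gestational age at delivery, true stays differ too, and the calculation above then shows dilution. Identical true stays with unequal transfer need another cause, such as place of delivery. Protocol 3.1.4 concerns data collection; it does not say that referring hospitals lack intensive care.

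Transfers would not be invisible. The stay after transport is to be reported, neonatal resource use is listed, and intensive care stay at birth is tabulated. None of these corrects the endpoint. With 97 women randomized, power on the assumed values is low under either definition.

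**Conclusion.** The point holds as a gap in the derivation. As written, the rule measures the birth admission only and, on the natural reading, truncates the stay of a newborn transferred to another hospital. Following it can reverse the order of a sick and a well infant. The likely consequence is loss of sensitivity: with sick newborns commoner in one arm, the ratio moved toward 1 throughout the range examined. A spurious difference is possible only if transfer differs between arms for other reasons.

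The size is unknown, because every transfer rate and length of stay used above is an assumption. The endpoint's importance rests on its key secondary status and its retained analysis in Table 2.301. A reader might take its first place in the sequential order to make it a gatekeeper, but SAP 5.2 removes the multiplicity adjustment, so that place should not be relied on.

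**What to change.** In SAP 11.5.4, define length of neonatal stay as the time from delivery to final discharge from hospital care, summing directly consecutive hospital stays, and state that a transfer is not a discharge. Use the transfer and second-facility stay already collected under Protocol 6.4.2.1. Because that item covers both other hospitals and extended stay facilities, say which of them count as hospital care.

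Before unblinding, also state how two other groups are scored: neonatal deaths, and infants still in hospital at 28 days after the estimated date of delivery, when Protocol 6.2.2 ends data collection. Neither has a defined discharge time under the current formula.

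Report the number of transferred infants by arm, and keep the birth-hospital stay as a descriptive line.

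The cost is a few sentences in the SAP and a derivation that adds existing fields. It needs no new data collection and no further patients.

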11.6. Appendix 6: Premature Withdrawals & Handling of Missing Data

11.6.1. Premature Withdrawals

Element	Reporting Detail
General	
 Subject study completion status was defined as subjects who either prematurely withdrawn. Those subjects that are randomized and not dosed are not considered as prematurely withdrawn. Subjects who are withdrawn from study participation after starting randomized treatment will not be replaced. Subjects who receive but who discontinue from IP will not be considered withdrawn from the study and should remain in the study and continue to be followed for efficacy and safety.

11.6.2. Handling of Missing Data

Element	Reporting Detail
General	
 Missing data occurs when any requested data is not provided, leading to blank fields on the collection instrument : 
 [1] These data will be indicated by the use of a “blank” in subject listing displays. [2] Answers such as “Not applicable” and “Not evaluable” are not considered to be missing data and should be displayed as such.

11.6.2.1. Handling of Missing Stratification

Element	Reporting Detail
GA at Randomization	
 If GA at randomization in weeks/days obtained from CRF is missing, the upper bound of the GA strata assigned at randomization will be used as a numeric value. For example, a subject in 24^{0/7} to 25^{6/7} group, 25 weeks and 6 days will be converted into numeric value.
Established Progesterone Use	
 Established progesterone use will be derived using medications which are taken prior to the study treatment and recorded in obstetrical medications CRF page. If a subject is stratified as progesterone user at the randomization but no progesterone medication prior to the study treatment was recorded in obstetrical medications CRF page, the subject will be considered as established progesterone user for analysis.

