5.3. Treatment Assignment

Subjects will be stratified by progesterone treatment and GA. The progesterone strata will consist of subjects on established progesterone therapy or subjects not on established progesterone therapy at Screening. The GA strata are $24^{0/7}$ to $25^{6/7}$, $26^{0/7}$ to $27^{6/7}$, $28^{0/7}$ to $30^{6/7}$, or $31^{0/7}$ to $33^{6/7}$. Subjects within each stratum will be randomly assigned in 1:1 ratio to receive either retosiban or atosiban using an interactive voice response system (IVRS)/interactive web response system (IWRS) in accordance with the randomization schedule.

Retosiban and atosiban regimens are described in [Table 3](#) and [Table 4](#). The IP will be administered by study personnel during each dosing session.

The time of dosing (i.e., start of the infusion) will be designated as time 0. All subsequent time points will be in relation to this time point. Infusion and dose administration information can be found in the SPM and Study Pharmacy Manual.

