5.7. Prior Medications and Nondrug Therapies

Prior medications will be reviewed and the investigator will attempt to obtain a complete history of any medications taken during the pregnancy (including the trimester of exposure, if possible) and during any previous episodes of preterm labor (e.g., magnesium sulfate for neuroprotection or antenatal corticosteroid treatment).

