2.3. Study Design

Overview of Key Study Design Features	
Design Features:	
 Phase III, randomized, double-blind, double-dummy, multicenter design Subjects are females, aged 18 to 45 years (Sweden) or aged 12 to 45 years (all other countries including UK, Germany, Italy, Israel, South Korea, Belgium, Mexico, Spain and Brazil), with an uncomplicated, singleton pregnancy and intact membranes in preterm labor between 24^{0/7} and 33^{6/7} weeks of gestation.
Dosing:	
 Retosiban treatment will be administered as a 6-mg IV loading dose over 5 minutes, followed by a 6-mg/hour continuous infusion over 48 hours. Atosiban will be given intravenously in 3 successive stages: an initial bolus dose of 6.75 mg using atosiban 6.75 mg/0.9 mL solution for injection, immediately followed by a continuous high dose infusion at 18 mg/hour for 3 hours, then a lower 6 mg/hour infusion for the remainder of the 48-hour treatment period using the atosiban 37.5 mg/5 mL concentrate for solution.
Treatment Assignment:	
 A total of 97 patients were blindly randomly assigned to retosiban or atosiban in a 1:1 ratio. Subjects were stratified by established progesterone treatment (Yes/No) and gestational age at randomization (24^{0/7} to 25^{6/7}, 26^{0/7} to 27^{6/7}, 28^{0/7} to 30^{6/7} and 31^{0/7} to 33^{6/7}). Subjects within each stratum will be randomly assigned in 1:1 ratio to receive either retosiban or atosiban using an IVRS in accordance with the randomization schedule.
Interim Analysis	
 The study was terminated before interim analysis due to feasibility. Details of the interim analysis were written in the IDMC RAP.

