5. GENERAL CONSIDERATIONS FOR DATA ANALYSES AND DATA HANDLING CONVENTIONS

5.1. Subgroups

5.1.1. Efficacy Analyses

The comparison of the treatment groups for the primary and selected secondary efficacy endpoints (i.e., prolongation of pregnancy, neonatal composite) will be analyzed by the following subgroups if applicable:

- GA at randomization with 4 categories: 24^{0/7} to 25^{6/7}, 26^{0/7} to 27^{6/7}, 28^{0/7} to 30^{6/7} and 31^{0/7} to 33^{6/7}
- Established progesterone group with categories “Yes” and “No”

In addition, for the primary efficacy endpoint, there are no per-protocol population defined, so additional subgroup analyses based on major protocol deviations or violation of PTL criteria (inclusion criteria #4) may be performed as appropriate. Also, additional subgroup analysis based on the status of spontaneous onset delivery will be performed.

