
 The primary endpoint of time to delivery will be statistically analyzed using a two-component finite mixture regression model. Time to delivery (y) is assumed to follow a mixture of two-components with normal densities. Within each component, the expected time to delivery will be modeled as a function of treatment (TRT) as fixed effect, and GA at randomization (GA) and established progesterone use (EP) as covariates., $f(y) = \sum_{k=1}^2 \pi_k(\mathbf{Z}, \alpha_k) N(\mu_k, \sigma_k^2),$ 
where $k = 2$ to denote the 2 groups of mothers namely those who deliver preterm and those who deliver at term.
 
The component normal distributions depend on the regressors: TRT, GA and EP thru the means μ_k, i.e.,
 $\mu_k = \beta_{0k} + \beta_{1k} \cdot \text{trt} + \beta_{2k} \cdot \text{GA} + \beta_{3k} \cdot \text{EP}, \pi_k(\text{trt}, \text{GA}, \text{EP}, \alpha) > 0 \quad \forall k, \sum_{k=1}^2 \pi_k(\text{trt}, \text{GA}, \text{EP}, \alpha) = 1$ 
The mixing probabilities π_k, which are non-negative and sum to one, are modeled using a logistic regression model with TRT, GA and EP and corresponding parameters, α, i.e,
 $\pi_1(\text{trt}, \text{GA}, \text{EP}, \alpha) = \frac{\exp(\alpha_0 + \alpha_1 \cdot \text{trt} + \alpha_2 \cdot \text{GA} + \alpha_3 \cdot \text{EP})}{1 + \exp(\alpha_0 + \alpha_1 \cdot \text{trt} + \alpha_2 \cdot \text{GA} + \alpha_3 \cdot \text{EP})}$ $\pi_2(\text{trt}, \text{GA}, \text{EP}, \alpha) = 1 - \pi_1(\text{trt}, \text{GA}, \text{EP}, \alpha)$ 
The patient assignment of each component is determined by the mixture model described

Primary Statistical Analysis							

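### Established progesterone use is rebuilt from pre-dose CRF records, so the covariate and subgroup may not match the factor stratified on, and any mismatch can only add women to the yes group

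*SAP*

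**What the plan says.** Protocol 5.3 defines the stratification factor by current status: "The progesterone strata will consist of subjects on established progesterone therapy or subjects not on established progesterone therapy at Screening". Protocol 5.8.1.3 fits this reading. It lets women already on established therapy continue and bars starting progesterone after enrolment.

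SAP 11.6.2.1 defines the analysis variable by a record: "Established progesterone use will be derived using medications which are taken prior to the study treatment and recorded in obstetrical medications CRF page". The next sentence gives the only reconciliation rule. "If a subject is stratified as progesterone user at the randomization but no progesterone medication prior to the study treatment was recorded" on that page, then "the subject will be considered as established progesterone user for analysis". No condition is set on duration, or on use continuing at Screening. The section is headed as dealing with missing stratification, but the progesterone rule is not limited to missing values. The gestational age (GA) rule beside it is: it falls back on the randomised stratum only when the CRF value is missing.

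EP is then used widely. SAP 7.1.2 models each component mean with "GA at randomization (GA) and established progesterone use (EP) as covariates" and also puts EP in the mixing probability. It is a covariate in the key secondary models (8.1.2, 11.7.2, 11.7.4). It defines one of the two named efficacy subgroups in 5.1.1 ("Established progesterone group with categories" yes and no), shown in displays 2.52, 2.152, 2.202 and 2.322. SAP section 9, which lists departures from the protocol, does not mention the derivation.

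**The concern.** Two things changed between design and analysis. The time anchor moved from status at Screening to anything recorded before dosing. And the reconciliation is one-sided: a CRF record can turn a stratum *no* into *yes*, but the absence of a record cannot turn a *yes* into *no*.

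If women move, the *yes* subgroup mixes those stratified as on therapy with those who were not. Its tables would then not describe the group the trial stratified. The treatment-by-EP term is exposed as well, because it is kept or dropped on a significance test (0.05 in SAP 7.1.2, 0.1 in 8.1.2). Misclassification could therefore affect which model is reported. The covariate adjustment would also no longer be for the factor balanced by design.

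**Working it through.** No power, sample size or alpha figure in the documents depends on this rule, so there is no stated figure to reproduce. The check has three parts.

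**1. The rule as a truth table** (SAP 11.6.2.1)

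| Randomised stratum | Pre-dose CRF record | Analysis EP | Basis |
|---|---|---|---|
| no | no | no | CRF derivation |
| no | yes | yes | CRF derivation, by implication |
| yes | no | yes | explicit override |
| yes | yes | yes | both agree |

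So EP = stratum *yes* OR CRF record. Only the second row changes the randomised value, and it moves women from *no* to *yes*.

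**2. How many could move.** N = 97 randomised (SAP 2.3). The documents give neither p, the share stratified *yes*, nor q, the share of the *no* stratum with a record. Both are assumed: p from 5% to 20%, q from 0 to 20%.

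- Stratum *yes* = N × p
- Moved = N × (1 − p) × q
- Share of analysed *yes* from the *no* stratum = moved / (stratum *yes* + moved)

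Example with p = q = 10%: 97 × 0.10 = 9.7; 97 × 0.90 × 0.10 = 8.7; 8.7 / 18.4 = 47%.

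| p (stratum *yes*) | q = 0 | q = 5% | q = 10% | q = 20% |
|---|---|---|---|---|
| 5% (4.9) | 0; 0% | 4.6; 49% | 9.2; 66% | 18.4; 79% |
| 10% (9.7) | 0; 0% | 4.4; 31% | 8.7; 47% | 17.5; 64% |
| 20% (19.4) | 0; 0% | 3.9; 17% | 7.8; 29% | 15.5; 44% |

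Each cell gives women moved, then their share of the analysed *yes* group.

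**3. Effect on the overall comparison.** This is an illustrative ANCOVA simulation with 3000 runs per setting, adjusting for GA and either the true stratum or the derived EP. From Protocol 8.2.1: GA strata of 7, 13, 27 and 53%, and 55% delivering within 3 weeks (applied here to both arms). Assumed: early deliveries uniform over 21 days, the rest around 39 weeks with SD 8 days, p = q = 10%, and a progesterone effect of 0 or 15 days in stratum *yes* women only.

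| N | Progesterone effect (days) | Type I error, stratum / derived | Power at 9.5 days, stratum / derived | SE under the null (days), stratum / derived |
|---|---|---|---|---|
| 97 | 0 | 0.051 / 0.050 | 0.401 / 0.401 | 5.459 / 5.472 |
| 97 | 15 | 0.044 / 0.045 | 0.405 / 0.405 | 5.450 / 5.500 |
| 300 | 0 | 0.047 / 0.049 | 0.871 / 0.870 | 3.109 / 3.112 |
| 300 | 15 | 0.047 / 0.050 | 0.854 / 0.852 | 3.104 / 3.129 |

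The Monte Carlo error on a 5% rate is √(0.05 × 0.95 / 3000) ≈ 0.004, so the type I errors cannot be told apart. The largest loss of precision is 5.500 / 5.450 = 1.009, under 1%. The simulation uses ANCOVA, not the mixture model, and includes no treatment-by-progesterone interaction.

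**The case against.** Several points on the other side are sound.

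- **The wording may be a data source, not a full algorithm.** The SAP does not say that any progesterone counts; that follows only from the absence of a restriction. The *no*-stratum-with-record cell is likewise implied, not stated. SAP section 3 leaves derivation details to an ADaM specification that is not in the documents and might add a condition.
- **The vivid example is unsupported.** A reader might infer that a woman who took progesterone only in the first trimester, for instance after IVF (eligible under inclusion criterion 3), becomes an established user. Protocol 5.7 does ask for a full pregnancy medication history, but EP is drawn only from the obstetrical medications page. The SAP summarises and lists those medications separately (6.5, Appendix 11). Nothing shows that stopped early courses reach that page.
- **A recent first dose proves no mismatch.** Neither document defines established, so a site could have stratified that woman *yes*.
- **The explicit override is reasonable.** A missing record does not prove non-use, and keeping the stratum there is what the fix also does.
- **CRF values are a legitimate choice.** Protocol 8.3.5.1.1 names established use as the covariate, not the stratum as randomised, and GA is also taken from the CRF. Women enrol in an emergency, sometimes without records, so stratification errors are foreseeable.
- **The subgroup tables carry limited weight.** The trial stopped at 97 women, and SAP 7.1.2 makes the time-to-delivery subgroups descriptive.

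What remains is the text itself. The anchor differs from the one stratified on, the correction works in one direction only, and section 9 does not declare it. A legitimate correction of stratification errors would use the Screening anchor and run both ways.

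**Conclusion.** The point holds as a mismatch of definition. Analysis EP may differ from the stratified factor, and any difference enlarges the *yes* group. The actual size is unknown: under the assumed ranges, 0 to about 18 of 97 women move and make up 0 to 79% of the analysed *yes* group. Zero is compatible with the documents.

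A reader might infer that the primary comparison is biased or underpowered as a result. The documents do not support that. EP describes pre-dose status in a blinded trial, and the simulation shows type I error and power essentially unchanged, subject to its assumptions and its use of ANCOVA. The consequence is mainly for interpreting the progesterone subgroup tables and the treatment-by-EP interaction. This is a cheap improvement, not a threat to the main result.

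**What to change.** In SAP 11.6.2.1, set EP to the progesterone stratum assigned at randomisation, for all models and subgroup tables. The section's own fallback rules already rely on the assigned strata, so the analyst has them.

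As a sensitivity analysis, define a CRF-derived EP as progesterone started before Screening and still ongoing at Screening, and let it correct the stratum in both directions. Add a cross-tabulation of stratum by CRF-derived value and list the discordant women, which replaces the assumed frequencies above with real ones. If the CRF-based value is kept as the main one, state the Screening condition and the rule for each discordant cell, and add the change to section 9.

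The cost is one paragraph and one derivation rule before unblinding, with no new data if the obstetrical medications page carries start and stop dates (an assumption). SAP 11.6.2.2 already sets rules for partial and missing medication dates. The downside is that errors made when stratifying at randomisation remain in the main analysis; the sensitivity analysis and cross-tabulation would show how much they matter.
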